2.4.5.3 Deaths

The following summaries of deaths will be generated.

- Number (%) of patients who died by study period (on-study, on-treatment, post-study)
- Deaths in nonrandomized patients or randomized but not treated patients
- Treatment-emergent adverse events leading to death (death as an outcome on the adverse event case report form page as reported by the Investigator) by primary SOC, HLGT, HLT, and PT showing number (%) of patients sorted by internationally agreed SOC order, with HLGT, HLT, and PT presented in alphabetical order within each SOC.

2.4.5.4 Analyses of laboratory variables

Laboratory parameters will be grouped and summarized by biological function as described in [Section 2.1.5.2](#).

The summary statistics (including number, mean, median, Q1, Q3, standard deviation, minimum and maximum) of all laboratory variables (central laboratory values and changes from baseline) will be calculated for each visit or study assessment (screening, run-in, baseline, postbaseline time point, last on-treatment value) by treatment group.

The incidence of PCSAs (list provided in [Appendix A](#)) at any time during the treatment-emergent adverse event period will be summarized by biological function and treatment group whatever the baseline level and/or according to the following baseline status categories:

- Normal/missing
- Abnormal according to PCSA criterion or criteria

For parameters for which no PCSA criteria are defined, similar table(s) using the normal range will be provided.

All measurements collected during the TEAE period, including values from unscheduled visits, will be considered for the PCSA summaries. These summaries will include patients in the safety population who have at least 1 assessment performed during the TEAE period. When a PCSA definition involves a change from baseline value, patients must also have a baseline value to be included in the summaries, and when required by the definition of the abnormality, patients must also have available laboratory normal ranges.

A listing of patients with at least 1 post-baseline PCSA (or out of normal range when no PCSA criterion is defined) will be provided which will display the entire patients' profile across time for all parameters belonging to the corresponding biological function. Individual data listings will include the following flags when applicable:

- Baseline values will be flagged "B".
- Normal laboratory ranges, available for most laboratory parameters, will be identified as ULN and LLN. Baseline, last on-treatment value, and individual data will be flagged "L" if the value is below the LLN and will be flagged "H" if it is above the ULN.
- Laboratory PCSA criteria will be used for the corresponding laboratory parameters. Values reaching a PCSA limit will be flagged (+, ++, -, or -- depending upon the direction and level of the abnormality). Flags for WBC and differential counts will be determined using data expressed in international units.

For parameters whose PCSA criteria are multiples of the ULN, the parameter's value will also be expressed as a multiple of the ULN in the individual data provided.

Drug-induced liver injury

The liver function tests, namely AST, ALT, alkaline phosphatase, and total bilirubin, are used to assess possible drug-induced liver toxicity. The proportion of patients with PCSA values at any postbaseline visit by baseline status will be displayed by treatment group for each parameter. The proportion of patients with PCSA values at any postbaseline visit will also be displayed by duration of exposure for each treatment group (only if a tabulation summary is necessary).

Listing of possible Hy's law cases identified by treatment group (eg, patients with any elevated ALT > 3 x ULN, and associated with an increase in bilirubin ≥ 2 x ULN) with ALT, AST, alkaline phosphatase, total bilirubin, and the following complementary parameters (if available): conjugated bilirubin and prothrombin time/international normalized ratio, creatine phosphokinase, serum creatinine, complete blood count, anti-HAV IgM, anti-HBc IgM, anti-HCV and HCV RNA, anti-CMV IgM and anti-HEV IgM antibodies, auto-antibodies: anti-nuclear, anti-DNA, anti-smooth muscle, Epstein-Barr virus, herpes viruses, and anti-LKM.

2.4.5.5 Analyses of vital sign variables

The summary statistics (including number, mean, median, Q1, Q3, standard deviation, minimum and maximum) of heart rate, temperature and respiratory rate (observed values, or mean of observed values, and changes from baseline) will be calculated for each visit or study assessment (baseline, each postbaseline time point, last on-treatment value) by treatment group.

The incidence of PCSAs at any time during the TEAE period will be summarized by treatment group for SBP, DBP and HR. All measurements collected during the TEAE period, including values from unscheduled visits, will be considered for the PCSA summaries. The summaries will include patients in the safety population who have at least 1 assessment performed during the TEAE period. When a PCSA definition involves a change from baseline value, patients must also have a baseline value to be included in the summaries.

A listing of patients with at least 1 post-baseline PCSA will be provided and will display the patient's profile over time of all vital sign parameters. Individual data listings will include the following flags:

- Baseline values will be flagged "B",
- Parameter values reaching a PCSA limit will be flagged (+, or - depending of the direction).

2.4.5.6 Analyses of electrocardiogram variables

Shift tables will be provided to present ECG status according to baseline status (Normal/Missing, Abnormal) for each treatment group during the TEAE period. Supportive listings of patients with abnormal ECG status at any post-baseline visit will be provided.

2.4.5.7 Analyses of physical examination variables

Shift tables will be provided to present physical examination findings by body system according to baseline status (Normal/Missing, Abnormal) for each treatment group during the TEAE period. Supportive listings of patients with abnormal findings at any post-baseline visit will be provided.

2.4.6 Analyses of pharmacokinetic variables

Plasma concentrations of sotagliflozin and its 3-O-glucuronide metabolite will be summarized by visit and nominal sampling time (pre-dose at Weeks 4, 18, 26 and 52) in the PK population (see [Section 2.3.3](#)) in the sotagliflozin group, using descriptive statistics such as number, geometric mean, coefficient of variation, median, minimum and maximum. Individual plasma concentrations of sotagliflozin and its 3-O-glucuronide metabolite at nominal sampling times will also be listed.

2.4.7 Analyses of patient reported outcomes**2.4.7.1 Scoring methods****TRIM-D is scored [1] in the following steps:**

Step 1: Reverse the scale of the 17 items that need to be reverse coded (see [Table 4](#)).

Step 2: Sum the raw score across items in each domain for domain scores and the raw score of all items for total score.

Note: A domain score is calculated if at least half of the items in a multi-item domain are answered (or half plus 1 in the case of domains with an odd number of items). Total score is calculated if 14 or more items are answered.

Step 3: Transform the raw score to a score ranging from 0 (worst) to 100 (best) using the following:

$$\text{Domain score} = [(\text{raw score} - \text{lowest possible raw score}) / \text{possible raw score range}] * 100$$

Lowest possible raw score and possible raw score range are provided in [Table 5](#).

Table 5 - TRIM-D range of scores

Domains	Cluster of Items	Lowest / Highest possible raw scores	Possible raw score range
Treatment Burden	1a, 2a, 2b, 2c, 2d, 2e	6/30	24
Daily Life	3a, 3b, 5a, 5b, 5c	5/25	20
Diabetes Management	4a, 4b, 4c, 4d, 4e	5/25	20
Compliance	6a, 6b, 6c, 6e	4/20	16
Psychological Health	6d, 7a, 7b, 7c, 7d, 7e, 7f, 7g	8/40	32
Total	All items	28 / 140	112

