9.3.3.2 Treatment related impact measure for diabetes (TRIM-D)

The TRIM-D is a validated questionnaire assessing the treatment-related impact on patients of diabetes medication (19). The TRIM-D questionnaire (Appendix B) is a 28-item measure with 5 domains assessing Treatment Burden, Daily Life, Diabetes Management, Compliance, and Psychological Health. The Diabetes Management domain evaluates the patient satisfaction with his/her medication's ability to control their diabetes, hyperglycemia, hypoglycemia, weight, and fatigue. A total score as well as 5 domain scores can be calculated. After reverse coding of some items, raw scores are calculated by summing the items. Then, the raw scores can be transformed to scores ranging from 0 to 100 with higher scores indicating less treatment impact.

The TRIM-D includes questions related to satisfaction with weight and hypoglycemia

The TRIM-D will be completed by all patients in the local language. The patients will be asked to complete the TRIM-D at Screening (Visit 1), Baseline (Visit 6, Day 1), Week 18 (Visit 12), Week 26 (Visit 13), Week 39 (Visit 14), and Week 52 (Visit 15). This should take less than 5 minutes for patients to complete.

The patients will be requested to complete the TRIM-D questionnaire by themselves during the selected clinical visits, independently from investigator, site staff, and any help from friends or relatives. For validity purposes, patients will be asked to answer all the questions of the questionnaires at the start of the visit before any other procedures or tests, in a quiet place, and while on site to return the completed questionnaires to the investigator or his/her designee on the same day.

[REDACTED]

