2.1.6.2 Treatment related impact measure for diabetes (TRIM-D)

The general treatment-related impact on patients’ health related quality of life (HRQoL) will be assessed using the TRIM-D questionnaire. The TRIM-D questionnaire is a 28-item measure comprising of 5 domains: Treatment Burden, Daily Life, Diabetes Management, Compliance, and Psychological Health (1). Table 4 below presents further technical details on this questionnaire.

Items are answered on a 5-point Likert scale ranging from (1) Not at all satisfied/convenient, or Never/Almost never, or Never/Almost never interferes to (5) Extremely satisfied/convenient, or Almost always/Always, or Almost always/Always interferes. Scales are converted into a score valued from 0 to 100 so that a higher score indicates a better health state (less negative impact). Score for each domain (called “domain score”) and total score are computed. See Section 2.4.7 for more details on the scoring method.

The TRIM-D variables include TRIM-D scores (total and domain scores) and the change in TRIM-D scores from baseline to endpoint.

Table 4 - TRIM-D domains and clusters

Domains	Number of Items	Cluster of Items	Item Reversion	Direction of Domains
Treatment Burden	6	1a, 2a, 2b, 2c, 2d, 2e	No	Higher score = better health state (less negative impact)
Daily Life	5	3a, 3b, 5a, 5b, 5c	Yes, for all items	
Diabetes Management	5	4a, 4b, 4c, 4d, 4e	No	
Compliance	4	6a, 6b, 6c, 6e	Yes, for all items	
Psychological Health	8	6d, 7a, 7b, 7c, 7d, 7e, 7f, 7g	Yes, for all items	

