2.5.3 Missing data

For categorical variables, patients with missing data are not included in calculations of percentages unless otherwise specified. When relevant, the number of patients with missing data is presented.

Derived variables will be considered missing if any of the original variables required to calculate them are missing. For example, if either a baseline assessment or an endpoint assessment is missing for a particular patient, then change from baseline at endpoint will be missing. Depending upon the assessment, analyses may not include all patients in the analysis population, because certain patients in the intended population may have missing data.

Incomplete date of first administration of double-blind IMP

Date/time of first administration is the first non-missing start date/time of double-blind IMP completed in the e-CRF “First dose IMP” module.

For patients who are randomized and dispensed a double-blind treatment kit but who are lost to follow-up just after Visit 6 (eg. only the treatment kit number is reported in the e-CRF “Exposure

- treatment period” module without any dose information), the date of first administration will be imputed using the date of randomization. When a patient is randomized but not exposed, “Not taken” should be ticked in the e-CRF “First dose IMP” module.

Handling of computation of treatment duration if IMP end of treatment date is missing

For the calculation of the treatment duration, the date of the last dose of double-blind IMP is equal to the date of last administration reported on the e-CRF “Treatment status library” page. If this date is missing, the exposure duration should be left as missing.

The last dose administration should be clearly identified in the case report form and should not be approximated by the last returned package date.

Handling of medication missing/partial dates

No imputation of medication start/end dates or times will be performed. If a medication date or time is missing or partially missing and it cannot be determined whether it was taken prior or concomitantly, it will be considered a prior, concomitant, and post-treatment medication.

Handling of adverse events/hypoglycemia with missing or partial date/time of onset

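### TRIM-D scoring allows unanswered items but sums and rescales as if every item were answered, so a permitted skip lowers the domain and total scores

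*SAP*

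**What the plan says.** SAP 2.1.6.2 describes the instrument: "The TRIM-D questionnaire is a 28-item measure comprising of 5 domains", each item is scored 1 to 5, and "Scales are converted into a score valued from 0 to 100". SAP 2.4.7.1 gives the scoring in three steps.

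- Step 1 reverses 17 items.
- Step 2 reads "Sum the raw score across items in each domain for domain scores and the raw score of all items for total score". Protocol 9.3.3.2 agrees: "After reverse coding of some items, raw scores are calculated by summing the items".
- A note under Step 2 sets the completeness rule: "A domain score is calculated if at least half of the items in a multi-item domain are answered", with half plus one for domains that have an odd number of items. For the total, "Total score is calculated if 14 or more items are answered".
- Step 3 subtracts the lowest possible raw score and divides by the possible range, both read from Table 5, to reach a 0-100 scale.

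SAP 2.5.3 has a general rule: "Derived variables will be considered missing if any of the original variables required to calculate them are missing". SAP 2.4.7.2 imputes missing post-baseline TRIM-D scores, then fits an ANCOVA of change to Week 52 with the Baseline score as covariate, reporting treatment differences and 95% CIs. SAP 2.1.3.3 and Protocol 9.1.3 single out the Diabetes Management domain for special attention.

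**The concern.** Three stated rules do not fit together: a plain sum, permission to score incomplete forms, and rescaling constants that assume a complete form. No step covers the skipped item; there is no proration, no person-mean substitution and no adjusted constant. A programmer who follows the text literally sums the answered items, so each skip counts as zero on a scale whose lowest value is 1.

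A skip at Week 52 then looks like worsening. A skip at Baseline looks like improvement and also puts a wrong value in the covariate. Similar skipping at both visits largely cancels in the mean change but adds noise. Artefactual or negative values would also reach the reported minima and the cumulative distribution plots.

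Two related ambiguities add to this. The general rule in SAP 2.5.3 would make any score with a skipped item missing, which would leave the note without effect; the SAP does not say which prevails. And half plus one of 5 items is 3.5, which can be taken as 3 or 4.

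**Working it through.** **Inputs.** Items run from 1 to 5 (SAP 2.1.6.2). Item counts are 6, 5, 5, 4 and 8, total 28 (SAP Table 4). Lowest scores and ranges come from SAP Table 5.

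**Reproducing Table 5.** With all n items answered, lowest = n, highest = 5n and range = 4n. All six rows reproduce, as do the 17 reversed items (5 + 4 + 8). The printed constants are right for complete forms, and only for those.

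**Formulas.** Let k of n items be answered with mean m after reversal.

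- As written: (k·m - n)/(4n) × 100
- Prorated (mean of answered items × n, same constants): (m - 1)/4 × 100
- Shortfall against prorated: m(n - k)/(4n) × 100, always positive because m is at least 1
- As-written score below 0 when m < n/k: 1.25 for 4 of 5 answered, 2.0 for 14 of 28

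As an exhaustive check on a 5-item domain, all 3,125 answer patterns with each of the 5 possible single skips (15,625 cases) gave a score below both the complete and the prorated score.

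**One skip, other items at 4 (complete or prorated score 75).**

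| Score | n | Lowest / range | As written | Loss |
|---|---|---|---|---|
| Treatment Burden | 6 | 6 / 24 | 58.3 | 4/24 = 16.7 |
| Daily Life | 5 | 5 / 20 | 55 | 4/20 = 20 |
| Diabetes Management | 5 | 5 / 20 | 55 | 4/20 = 20 |
| Compliance | 4 | 4 / 16 | 50 | 4/16 = 25 |
| Psychological Health | 8 | 8 / 32 | 62.5 | 4/32 = 12.5 |
| Total | 28 | 28 / 112 | 71.4 | 4/112 = 3.6 |

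**Diabetes Management, 4 of 5 answered** (allowed whether the threshold is 3 or 4):

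- all at 5: (20 - 5)/20 = 75 instead of 100
- all at 4: (16 - 5)/20 = 55 instead of 75
- all at 1: (4 - 5)/20 = -5 instead of 0

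**Total, 14 of 28 answered:**

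- all at 5: (70 - 28)/112 = 37.5 instead of 100
- all at 4: (56 - 28)/112 = 25 instead of 75
- all at 1: (14 - 28)/112 = -12.5 instead of 0

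**Effect on group summaries.** The documents give no skip rate and no TRIM-D SD, so the rates here are assumptions. Suppose a proportion p of patients skip one Diabetes Management item at a visit, with the others at 4, so that each skip costs 20 points. That visit's mean falls by 20p and its variance rises by about 400p(1 - p).

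| p | Fall in mean | Added variance (points squared) |
|---|---|---|
| 1% | 0.2 | 3.96 |
| 5% | 1.0 | 19 |
| 10% | 2.0 | 36 |

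The treatment contrast shifts by 20 × the between-arm difference in Week 52 skip rate: 0.2 points for 1 percentage point, 1.0 for 5. Baseline precedes randomization, so Baseline skips are balanced between arms in expectation.

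**The case against.** The strongest reply is that the SAP leaves the rule unstated rather than stating a wrong one. It cites the instrument booklet as reference 1, which may contain the item rule, and its own 0-100 range argues against summing only the answered items. That is fair as far as it goes: the booklet is not available here and may settle the matter. But the SAP writes the scoring out as explicit steps, and those steps contain a sum, a tolerance for skips and full-form constants. A reader who follows them gets the wrong score, and the broken range shows that the text is inconsistent with itself.

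Second, SAP 2.5.3 refers to variables required for the calculation, and the TRIM-D note can be read as defining what is required, so the specific rule would override the general one. That is a reasonable reading, but the SAP does not state it. If the note prevails, the under-summing follows; if 2.5.3 prevails, the note does nothing.

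Third, Protocol 9.3.3.2 has patients asked to answer every question, on site and before other procedures. This should keep skips few, but it does not correct the formula when one occurs.

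Fourth, equal skipping in the arms does not give exactly zero shift, because the loss grows with the item values. For a 5-item domain with equal skip probability p and true contrast D, the shift is -pD/5, or 1% of D at p = 5%. This is correct and negligible; a zero expected shift holds exactly only when the arms have equal means.

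**Conclusion.** The concern holds. Applied as written, the scoring lowers a domain score and the total whenever a permitted skip occurs, and it can produce values below 0. With the other items at 4, one skip costs 12.5 to 25 points in the affected domain and 3.6 in the total; other domains are untouched. The direction is certain because no item scores below 1. The multiple imputation in SAP 2.4.7.2 does not help, since it fills absent scores and leaves under-summed ones alone.

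The effect on the treatment comparison depends on skip rates that the documents do not give; the 0.2 to 1.0 point shift rests on the assumed between-arm differences above. TRIM-D is an other endpoint outside the fixed testing sequence, so no confirmatory conclusion depends on it. It should still be corrected before scoring, because estimates with confidence intervals will be reported and two programmers could derive different data from the same text.

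**What to change.** Make three additions to the SAP:

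1. In Step 2 of 2.4.7.1, after checking the booklet cited as reference 1, define the raw score as the mean of the answered items times the number of items in the domain (or 28 for the total), whenever the minimum-answered rule is met. Step 3 and Table 5 stay as they are, and every score stays within 0-100.
2. State whether a 5-item domain needs 3 or 4 answered items.
3. State that the any-component-missing rule in 2.5.3 does not apply to TRIM-D scores.

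The cost is three sentences and one line of code. The drawback is that proration assumes skipped items resemble answered ones. This is weakest for the total: Treatment Burden (6) plus Psychological Health (8) already reaches 14, so a total could be scored with Daily Life, Diabetes Management and Compliance wholly unanswered.

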2.4.7.2 Analysis methods

The analysis of the TRIM-D PRO scores will be conducted on the ITT population.

For TRIM-D scores (total and domain scores), descriptive statistics (mean, median, SD, minimum and maximum) for absolute values and for changes from baseline will be presented by treatment group at baseline, Week 18, Week 26, Week 39 and Week 52.

The change in TRIM-D scores from Baseline to endpoint will be analyzed using a similar approach to the primary efficacy endpoint, with missing post-baseline values imputed by the retrieved dropouts imputation method or by the washout imputation method according to the criterion described in [Section 2.4.4.1](#).

After the imputation, each of the complete datasets will be analyzed by the ANCOVA model with treatment groups (sotagliflozin 400 mg, sotagliflozin 200 mg, placebo), randomization strata of Week -1 HbA1c ($\leq 8.5\%$, $> 8.5\%$), randomization strata of Week -1 SBP (< 130 mmHg, ≥ 130 mmHg), and randomization strata of sulfonylureas use at Week -1 (yes, no), and country as fixed effects, and TRIM-D scores at Baseline as a covariate. Results from each complete dataset will be combined to provide the adjusted mean change from Baseline to Week 52 for each treatment group, as well as the between group difference (comparing each sotagliflozin group versus placebo) and the 95% CI using contrast statements.

Cumulative distribution functions of scores change from baseline to endpoint will be displayed by treatment groups for TRIM-D scores (total and domain scores).

2.5 DATA HANDLING CONVENTIONS

2.5.1 General conventions

The following formulas will be used for computation of parameters.

HbA1c

The formula to convert HbA1c from Diabetes Control and Complications Trial (DCCT) aligned value to International Federation of Clinical Chemistry and Laboratory Medicine (IFCC) standardized value is,

$$\text{IFCC-HbA1c (mmol/mol)} = [\text{DCCT-HbA1c (\%)} - 2.15] \times 10.929.$$

Renal function formulas

The estimated GFR (mL/min/1.73 m²) will be calculated using the 4 variable Modification of Diet in Renal Disease (MDRD) formula:

$$\text{Standard unit: eGFR (mL/min/1.73 m}^2\text{)} = 175 \times [\text{Serum Creatinine } (\mu\text{mol/L})/88.4]^{-1.154} \times \text{Age (year)}^{-0.203} \times 1.212 \text{ (if Black)} \times 0.742 \text{ (if Female)}$$

$$\text{Conventional unit: eGFR (mL/min/1.73 m}^2\text{)} = 175 \times \text{Serum Creatinine (mg/dL)}^{-1.154} \times \text{Age (year)}^{-0.203} \times 1.212 \text{ (if Black)} \times 0.742 \text{ (if Female)}$$

UACR

Standard unit: $UACR (mg/g) = \text{Urine Albumin (mg/dL)} / [\text{Urine Creatinine (mmol/L)} \times 11.31] \times 1000$

Conventional unit: $UACR (mg/g) = \text{Urine Albumin (mg/dL)} / \text{Urine Creatinine (mg/dL)} \times 1000$

Calculation of LDL-C

When TG is lower than or equal to 4.52 mmol/L (400 mg/dL), LDL-C is calculated using the Friedewald equation as:

- in standard unit (mmol/L), $TC - HDL-C - TG/2.17$;
- in conventional unit (mg/dL), $TC - HDL-C - TG/5$.

